# 9. Safety Assessments and Procedures

Vital Signs: Vital signs will be assessed at study visits per Study Procedures Table (Attachment A). Blood pressure, heart rate, and oxygen saturation will be taken in a seated position or supine position after a rest period of five minutes.

Medical History: The subject's lifetime medical history will be taken during the screening period. Medical history includes previous and current diseases.

**Physical Examination:** A physical examination including a neurological examination, an assessment for breast tenderness and gynecomastia, thrombosis (e.g., calf tenderness, shortness of breath), and sexual dysfunction.

Electrocardiograph (ECG): A supine, 12 lead ECG will be performed according to the Study Procedures Table (Attachment A). Potentially clinically significant ECG abnormalities will be interpreted by a local cardiologist at the discretion of the Principal Investigator

# 10. Criteria for Repeat Assessments, Rescreening, and Discontinuation

### **Repeat Assessments**

Screening Window

-Screening assessments can be repeated within the screening window under the same screening number with the exception of eligibility criteria related rating scales/questionnaires. Subject diagnosis confirmation will not be repeated.

-Morning (6am-12pm) Total Testosterone (TT) Plasma Levels: As noted, TT will be assessed during screening.

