A comprehensive safety plan is included in protocol (see Section 9 below) to ensure the safety of subjects participating in Stage 2 and that the risk for "estrogen-like" adverse events including thromboembolic events is mitigated. It has been demonstrated in Lilly's Single Dose Escalating Study (BPAC) that LY500307 related TT suppression occurs relatively rapidly. Therefore, potential cases of TT suppression in this study will be likely detected at week 1 (Visit 2.5), the first post-randomization TT assessment point. Importantly, this relatively short exposure interval and close monitoring of ER $\alpha$  engagement greatly reduces the possibility of experiencing adverse events, particularly an estrogen-like induced thromboembolic event. Moreover, related to the risk that higher dose estrogen preparations have greater thrombogenic potential than lower doses, this risk factor is addressed in the current protocol by purposely dosing LY500307 to avoid ER $\alpha$  receptor binding and thus negating the effects of full estrogen-like receptor activation that occurs with high dose estrogen preparations. In addition, ER $\alpha$  engagement is closely monitored with serial TT sampling. TT and safety will be assessed at screening, baseline, and weeks 1, 2, 4 and 8 during the treatment phase of the study.

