#### Rationale for Primary Endpoints

Primary Aim 1: fMRI/N-back was selected as the primary biomarker of cortical target engagement because it has been shown to be sensitive to estrogen (11) and numerous studies have consistently demonstrated that this paradigm demonstrates abnormal frontal and parietal activation in schizophrenia.(42-45)

Primary Aim 2: The Negative Symptom Assessment Scale – 16-item (NSA-16) is a commonly used, validated instrument for assessing negative symptoms in schizophrenia clinical trials (46). The three cognitive tests were chosen because 1) the literature indicates they are sensitive to estrogen (5), 2) they reflect core cognitive impairment in schizophrenia (47) and 3) they are contained in the Measurement and Treatment Research to Improve Cognition in Schizophrenia (MATRICS) Consensus Cognitive Battery (MCCB) which has been validated for schizophrenia treatment trials and endorsed by NIMH and FDA for studies of cognitive impairment associated with this illness (48). The Hopkins Verbal Learning Test has 6 alternative forms to mitigate practice effects and the Letter Number Sequencing and Spatial Span tests have minimal practice effects after the first follow up testing session.

Primary Aim 3: Both estrogen therapy and ER $\alpha$  agonists, but not selective ER $\beta$  agonists, robustly suppress plasma testosterone levels (35, 36). Thus, decreases in plasma testosterone concentrations from baseline levels in the LY500307 arms would reflect ER $\alpha$  engagement. Although schizophrenia and antipsychotic drugs are not directly associated with altered testosterone levels (49), antipsychotics may increase plasma prolactin levels which could secondarily reduce plasma testosterone levels (50). In addition, other factors such as smoking status, age and obesity may influence testosterone concentrations (51). Thus each subject will be used as his own control in assessing LY500307 potential effects on this hormone to address the effects of potential confounds.

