#### **Discontinuation**

Subjects will be discontinued under the following circumstances:

- ECG: Any subject with an absolute QTc of 450 msec or greater or a change from baseline of 60 msec or greater during the active treatment phases
- Total Testosterone Suppression: Subjects with a 50% reduction from baseline post dosing downward titration (See Section 12) will have values reassessed within one week of receipt. If the retest value is also a 50% reduction from baseline, the subject will be discontinued.
- Study Medication Non-Compliance: Significant noncompliance is defined as missing > 7 consecutive days of study medication or > 20 cumulative doses during the entire study.

If a subject discontinues from the study, discontinuation assessments will be at the discretion of the principal investigator.

A subject may withdraw from the study medication at any time at his own request, or may be withdrawn at any time at the discretion of the principal investigator for safety, behavioral, or administrative reasons.

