### 11. Laboratory Assessments

Laboratory assessments (blood and urine) will be collected at time points specified in Study Procedures Table (Attachment A) and analyzed by a local laboratory with the exception of the urine dipstick assessments which will be collected and analyzed onsite.

A total of 26 mL of blood will be collected at Visit 1, 14 mL at Visit 2, 10 mL of blood at Visits 2.5 and 3, 17 mL at Visit 4 and 23 mL of blood at Visit 6.

Laboratory assessments to be completed:

complete blood count with differential (CBC w/diff) comprehensive metabolic panel (CMP) hepatitis panel hemoglobin A1c (HgbA1c) lipid panel testosterone plasma levels (Free and Total) thyroid stimulating hormone level (TSH) urine toxicology screen Luteinizing Hormone Prolactin

Version: 05.01.17 (Amendment L) Page 22 of 36 Pharmacokinetics (PK): Pharmacokinetic (PK) blood samples to determine LY500307 plasma concentration will be obtained according to the Attachment A. The exact time of the blood draws and dosing will be recorded.

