### Stage 2 Dosing Downward Titration

If total testosterone suppression is confirmed during the study (a 50% reduction from baseline post randomization), subjects will be blindly switched to the next lowest dosing arm for the remainder of the trial. Thus, a subject randomized to 150 mg/day will be titrated down to 75 mg/day, and those randomized to 75 mg/day will be titrated down to placebo, and those randomized to placebo will continue on placebo.

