### ATTACHMENT A

Study Procedures Table

aHopkins Verbal Learning Test-Revised, Wechsler Memory Scale-Third Ed: Spatial Span, and Letter-Number Sequencing are included in the MCCB. At Visit 3 and 5 they will be administered separately from the full MCCB.

bIf Visit 2 occurs within 14 days from Visit 1, the following labs will NOT be repeated at Visit 2: Luteinizing Hormone, CBC w/ diff, CMP, Prolactin

cLabs and baseline assessments to be obtained pre-dose

dPK samples will be collected from all randomized subjects. PK samples will be collected at Visits 2.5, 3, 4, and 6. The exact time of the blood draws and dosing will be recorded.

eAll blood samples for clinical laboratories will be drawn in the morning after an 8-hour overnight fast

Baseline version of CSSRS will be conducted at the screening visit/Visit 1. The "Since Last Visit" version will be used on subsequent visits.

gBrief physical examination will be performed at Visits 2-5 including a general examination assessing for health changes, an assessment for breast tenderness, gynecomastia, sexual dysfunction, and thrombogenic events

hLifetime substance use will be captured at Visit 1.

iPre-existing medical conditions will be tracked as AE's at the discretion of the principal investigator.

Colicol		1 1 4010
Medication	Allowed	Notes
Amphetamines (e.g., methylphenidate, dextroamphetamine)	Yes-Conditional	Stable dose, no changes or additions for one week prior to screening and during the trial
Androgens	No	
Antiemetics with dopamine blocking	No	
properties (eg., metoclopramide, domperidone, others)		
Antiepileptic mood stabilizers	Yes	Stable dose, no changes or additions for one week prior to screening
Antihistamines, nonsedating (eg., loratidine, fexofenadine, cetirizine)	Yes	
Antihistamines, sedating (e.g.	Yes	Stable dose OR No use within 8 hours
diphenhydramine, hydroxyzine, meclizine, benztropine)		prior to cognitive assessments
Antipsychotic medications	Yes	
Barbiturates	No	
Benzodiazepines	Yes	Stable dose OR No use within 8 hours prior to cognitive assessments
Bupropion	Yes	Stable dose, no changes or additions for one week prior to screening
Corticosteroids (except topical, intranasal, or inhaled)	No	
Decongestants (eg., pseudophedrine)	Yes	Stable dose OR No use within 8 hours prior to cognitive assessments
Dicyclomine	No	
Estrogens	No	

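### Testosterone draws are not matched to each man's baseline clock time, and recording of the baseline time is not assured: a small average effect on the 50% rules, but a cheap one to remove

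*Combined protocol and SAP*

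**What the plan says.** Section 10 heads the testosterone item "Morning (6am-12pm) Total Testosterone (TT) Plasma Levels" under both the screening window and the post-randomization repeat assessments. The second entry only points to Section 12, which has no clock-time rule.

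Attachment A adds sampling conditions. The footnotes on the testosterone row say "All blood samples for clinical laboratories will be drawn in the morning after an 8-hour overnight fast" and "Labs and baseline assessments to be obtained pre-dose". On timing in the trial, Section 4 (Addressing Safety in Stage 2) states: "TT and safety will be assessed at screening, baseline, and weeks 1, 2, 4 and 8".

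The comparison is within subject. For Primary Aim 3, Section 4 (Rationale for Primary Endpoints) says: "Thus each subject will be used as his own control in assessing LY500307 potential effects on this hormone". Section 12 starts the blinded downward switch with "If total testosterone suppression is confirmed during the study (a 50% reduction from baseline post randomization". Section 10 (Discontinuation) ends its testosterone rule with "If the retest value is also a 50% reduction from baseline, the subject will be discontinued". Section 12 also drops 150 mg/day if five or more of the first ten men on that dose meet the suppression criterion.

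On recording, Section 11 says, under Pharmacokinetics, "The exact time of the blood draws and dosing will be recorded", and the pharmacokinetic footnote of Attachment A repeats it. Pharmacokinetic samples are taken at Visits 2.5, 3, 4 and 6, not at Visits 1 or 2.

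**The concern.** Restricting the sample to mornings implies that time of day matters, yet six hours is wide and the two samples in each comparison need not fall at the same point in it. Section 4 uses the own-control comparison to deal with smoking, age and obesity. Those are broadly stable within a man over eight weeks and largely cancel. Draw time can differ between a man's own samples and does not cancel.

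Confirming a fall reduces noise in the follow-up values, but both follow-up values are divided by the same baseline. If that baseline was unusually early or late, the retest inherits the same error.

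The 50% threshold feeds Primary Aim 3, the blinded dose switch, discontinuation and the 150 mg/day drop rule. None of these is adjusted for placebo, so misclassification near the cut-off goes directly into them. If the baseline clock time is not recorded, the size of the problem cannot be checked afterwards.

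**Working it through.** The plan gives no figure that depends on draw time, so there is none to reproduce. The check asks how far the 50% rule can move.

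**Inputs.**
- Window: 6 am to noon (Section 10).
- Threshold: a 50% fall from own baseline, confirmed (Sections 10 and 12). Arm rule: 5 of 10 (Section 12).
- Scatter: in Table 2 (Phase 2 study) the placebo mean at baseline is 517.1 ng/dL, and the SD of change is 117.9 at week 12 and 122.7 at week 24. As fractions of the mean, 117.9/517.1 = 0.23 and 122.7/517.1 = 0.24. A per-sample SD of 0.16 on the log scale gives √2 × 0.16 = 0.226 for a change, close to this.
- Decline D from 6 am to noon: **assumed** to be 10%, 20% or 30%. The documents give no value.

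**Step 1: the ends of the window, without noise.** Let s be the true drug fall. With baseline at 6 am and follow-up at noon, the reading is 50% when (1 − s)(1 − D) = 0.5, so s = 1 − 0.5/(1 − D). In the reverse order, (1 − s)/(1 − D) = 0.5, so s = 1 − 0.5(1 − D).

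| D | early baseline, late follow-up | late baseline, early follow-up |
|---|---|---|
| 10% | 1 − 0.5/0.9 = 44% | 1 − 0.5 × 0.9 = 55% |
| 20% | 1 − 0.5/0.8 = 37.5% | 1 − 0.5 × 0.8 = 60% |
| 30% | 1 − 0.5/0.7 = 29% | 1 − 0.5 × 0.7 = 65% |

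These are the most that one man's threshold can move under each D.

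**Step 2: draw times random in the window.** Log change = log(1 − s) + log(1 − D·u₁) − log(1 − D·u₀) + e₁ − e₀, with each u uniform on 0 to 1 and each e having SD 0.16. Two follow-up values share one baseline, and both must be at or below 50% of it. The arm rule is P(X ≥ 5) for X binomial with n = 10 and the confirmed probability.

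| | matched | D = 10% | D = 20% | D = 30% |
|---|---|---|---|---|
| SD of log change | 0.226 | 0.230 | 0.244 | 0.269 |
| Confirmed, true 30% fall | 1.9% | 2.0% | 2.5% | 3.4% |
| Confirmed, true 60% fall | 74% | 73% | 71% | 68% |
| 5 or more of 10, true 60% fall | 98% | 97% | 96% | 94% |

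The variance that matching would remove is 1 − (0.226/0.230)² = 3%, 1 − (0.226/0.244)² = 14% and 1 − (0.226/0.269)² = 29%. At a true 50% fall the arm rule is met with probability 21% whatever D is.

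**Step 3: no drug effect.** With random times, two readings at or below 50% occur in at most 0.05% of men for D up to 30%. Even if every baseline were at 6 am and every follow-up at noon, D = 30% gives about 2%, and 5 or more of 10 has probability below one in a million.

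**Step 4: a shift in one direction, D = 20%.**
- True 40% fall, all baselines at 6 am and all follow-ups at noon: confirmed in 41% against about 10% matched; arm rule about 38% against 0.1%.
- True 60% fall, the reverse order: confirmed in 33% against 74%; arm rule 21% against 98%.

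Using 0.23 instead of 0.226 as the SD of log change moves these results by about one percentage point at most.

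**The case against.** The strongest reply is that the plan already controls most of this. Samples are taken in the morning, fasting and pre-dose. A fall must be confirmed before it counts, and an arm is judged on five of ten men. The randomised placebo arm has the same draw-time variation, so a between-arm comparison of testosterone is not biased. There are two pre-dose samples, at screening and baseline, so an aberrant baseline could be noticed. All of this stands, except that the placebo arm does not protect the individual rules, and the plan does not say how the screening value would be used against an odd baseline.

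A reader might infer more: that the daily decline is being counted as drug suppression, or that a 29% drug fall will commonly read as 50%. The documents do not support either. They give no size for the decline and no sign that draw times drift one way, and Step 3 shows that time of day alone almost never gives confirmed suppression. Section 4 reports no evidence of suppression in the blinded Stage 1 data from 30 completed subjects. Nor does a 50% fall from baseline cover every testosterone rule: Section 4 describes an absolute 300 ng/dL discontinuation criterion for Stage 1.

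The scatter estimate is also open to challenge. It comes from men with median ages of about 64 to 67, against a Stage 1 mean of 33.9 years here, and it may already include that study's own draw-time variation. The 3% to 29% of removable variance is therefore only indicative.

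Finally, the silence about baseline draw time is a gap, not a contradiction. A 6 am to noon limit presumes that someone looks at the clock. It does not say that the time is kept.

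**Conclusion.** The point holds as a cheap improvement of low severity. The window is six hours wide, no matching is required, and recording of the baseline clock time is not assured, so a time-of-day difference enters the own-control 50% comparison in either direction and a retest cannot cancel the share that comes from the baseline.

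The average consequence is small: at most about 6 percentage points of confirmation for a true 60% fall, and about 4 points on the arm rule. Larger effects are confined to individual men near the cut-off, or to draw times that shift systematically, which nothing in the documents shows. The results rest on the assumed 10% to 30% linear decline, uniform draw times, the Phase 2 scatter, independent men, and a single pair of follow-up readings rather than the full visit schedule. The Stage 1 decision is not called into question.

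**What to change.** For Stage 2 draws from here on, in Section 10 and Attachment A:

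- Keep the morning window, and schedule each post-randomisation testosterone draw and any retest close to the subject's baseline clock time, for example within 1 to 2 hours. The width is a practical choice; the documents do not determine it.
- Record the clock time of every testosterone draw, including Visits 1 and 2 and unscheduled retests.
- In Section 16, use the difference in draw time from baseline as a covariate or in a sensitivity analysis for the continuous testosterone change only. It does not alter the threshold rules, which are helped only by the matched scheduling.

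The cost is one case report form field, a scheduling instruction and slightly less flexible morning appointments. No procedure is added and no clinical threshold changes.

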#### Post Randomization

-Morning (6am-12pm) Total Testosterone (TT) Plasma Levels: See Section 12, *Stage 2 Dosing Downward Titration* 

#### Rescreening

Subjects who screen fail may be rescreened one time, under a new screening number. If a subject is rescreened, all screening assessments (with the exception of the diagnosis confirmation) must be repeated and the stability criteria timelines must be met.

#### **Discontinuation**

Subjects will be discontinued under the following circumstances:

- ECG: Any subject with an absolute QTc of 450 msec or greater or a change from baseline of 60 msec or greater during the active treatment phases
- Total Testosterone Suppression: Subjects with a 50% reduction from baseline post dosing downward titration (See Section 12) will have values reassessed within one week of receipt. If the retest value is also a 50% reduction from baseline, the subject will be discontinued.
- Study Medication Non-Compliance: Significant noncompliance is defined as missing > 7 consecutive days of study medication or > 20 cumulative doses during the entire study.

If a subject discontinues from the study, discontinuation assessments will be at the discretion of the principal investigator.

A subject may withdraw from the study medication at any time at his own request, or may be withdrawn at any time at the discretion of the principal investigator for safety, behavioral, or administrative reasons.

### 11. Laboratory Assessments

Laboratory assessments (blood and urine) will be collected at time points specified in Study Procedures Table (Attachment A) and analyzed by a local laboratory with the exception of the urine dipstick assessments which will be collected and analyzed onsite.

A total of 26 mL of blood will be collected at Visit 1, 14 mL at Visit 2, 10 mL of blood at Visits 2.5 and 3, 17 mL at Visit 4 and 23 mL of blood at Visit 6.

Laboratory assessments to be completed:

complete blood count with differential (CBC w/diff) comprehensive metabolic panel (CMP) hepatitis panel hemoglobin A1c (HgbA1c) lipid panel testosterone plasma levels (Free and Total) thyroid stimulating hormone level (TSH) urine toxicology screen Luteinizing Hormone Prolactin

Version: 05.01.17 (Amendment L) Page 22 of 36 Pharmacokinetics (PK): Pharmacokinetic (PK) blood samples to determine LY500307 plasma concentration will be obtained according to the Attachment A. The exact time of the blood draws and dosing will be recorded.

### 12. Study Medication

Study medication will be taken by mouth once daily. During Stage 1 doses will consist of 25 mg, 75 mg, and placebo. During Stage 2, placebo, LY500307 75 mg/day, and LY500307 150 mg/day will be administered as six blinded study drug pills per day. LY500307 and matched placebo will be supplied by Lilly for the study. Placebo capsules will look like LY5000307, with matching shape, taste, and color. All study medication supplies will be labeled, stored, reconciled, and destroyed according to applicable regulatory requirements. A Certificate of Analysis, the expiry date, and a statement of GMP compliance will be supplied by Lilly.

### Stage 2 Dosing Downward Titration

If total testosterone suppression is confirmed during the study (a 50% reduction from baseline post randomization), subjects will be blindly switched to the next lowest dosing arm for the remainder of the trial. Thus, a subject randomized to 150 mg/day will be titrated down to 75 mg/day, and those randomized to 75 mg/day will be titrated down to placebo, and those randomized to placebo will continue on placebo.

#### Stage 2 Continued Dose Assessment

The first 10 subjects randomized to 150 mg/day will be reviewed by the Data Safety Monitoring Board (Section 15 below) to determine the safety of further randomizations at this dose. If five or more of 10 subjects randomized to 150 mg/day meet the TT suppression criteria as described in Section 12 above, that dose will be dropped from Stage 2 and all future newly randomized subjects will be randomized to placebo and 75 mg/day in a 1:1 fashion. (Note: ER $\alpha$  receptor engagement by LY500307 insures full engagement of ER $\beta$  receptors. Thus, if 150 mg/day proves to be a TT suppressing dose, these data provide support that the 75 mg/day dose is fully activating ER $\beta$  receptor as a target for innovative therapeutics for schizophrenia] will be achieved).

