	Erectile Dysfunction		1							
	Abdominal Discomfort				1					
ITA-IVIC-DPAF	Diarrhea				1					
I1A-JE-BPAG	None Reported									

Table 1. Summary of Adverse Events Possibly/Probably Related to LY500307 Treatment

Abbreviation: ID = identification; BM = bowel movement.

Data Source: Clinical Study Report for IIA-MC-BPAC; Clinical Study Report for IIA-MC-BPAD; Clinical Study Report for IIA-MC-BPAF; bpag\_v1\_tfls\_01dec201

ERß Selectivity and Effects on Testosterone: Non-selective estrogenic ligands (e.g., estrogen, estradiol, selective estrogen receptor modulators, SERMs) suppress the hypothalamus-pituitary-gonadal axis, resulting in decreases in testosterone and other reproductive hormone plasma levels (35, 36). The ER $\alpha$ , but not ER $\beta$ , receptor mediates the suppressing effects of these hormones (35, 36). Because testosterone suppression is mediated by ER $\alpha$  and it is associated with less intra-subject variability than other reproductive hormones (e.g., luteinizing hormone), plasma total testosterone levels have been used as a biomarker of central ERß selectivity in clinical trials. Preclinical studies demonstrated dose-dependent effects of LY500307 on plasma total testosterone concentrations with engagement of ER $\alpha$  at the higher doses tested. In the SDES, plasma total testosterone levels demonstrated significant dose-dependent decreases at doses at 25 mg and above (i.e., 125 mg, 250 mg and 500 mg). Effects at 25 mg were small (12% change from baseline). Testosterone suppression was reversible in all cases. In the 14-day MDES, testosterone suppression did not occur at any dose including the highest dose tested which was 100 mg/day. The mean change from baseline in plasma total testosterone levels (nmol/dL) between the 100 mg/day assigned group (N=6) and placebo assigned group (N=8) across all time points ranged from a difference of -2.50 (p=0.205) to 0.99 (p=0.621). In the Phase 2 BPH study (see below), there were no effects observed on total testosterone or other reproductive hormones at any dose including 25 mg/day which was the highest dose tested. These data suggest that 25 mg is an ER $\beta$  selective dose. The MDES provide support for ER $\beta$  selectivity at doses up to 100 mg/day.

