# 4. Study Design/Investigational Plan

A two-stage Phase 1b/Phase 2a adaptive ("drop the inferior dose") experimental design is ongoing that combines three studies (clinical dose optimization, cortical target engagement confirmation and efficacy and safety assessment) into a single clinical trial.

Stage 1 was conducted in year 1 and Stage 2 will be conducted in years 2 and 3. The goal of Stage1 was to identify and advance the highest dose that did not demonstrate a safety signal and had target selectivity as determined by lack of TT suppression. If these criteria were fulfilled at both doses, the larger of the two (75 mg/day dose) would be advanced to Stage 2. Furthermore, if there was no suggestion of ER $\alpha$  receptor activation (i.e., no pattern of TT decreases or feminization AEs) at either dose (25 mg/day and 75 mg/day), a third arm of 150 mg/day would be added to Stage 2 for evaluation. This scenario then results in the following three arms in Stage 2: placebo, 75 mg/day and 150 mg/day. The goals of stage 2 are to further assess LY500307 doses for safety and target selectivity, confirm cortical target engagement and assess efficacy.

In evaluating Stage 1 blinded safety and target selectivity (i.e., TT effects) data, the pattern of results (Tables 3, 4, and 5 above) suggest that both the 25 mg/day and 75 mg/day doses are safe and free of ER $\alpha$  receptor effects and would result in advancing the 75 mg/day dose to Stage 2. It should be noted that inspection of the blinded TT data from 30 completed subjects reveals that the TT suppression Go/No Go criterion, which requires five of 10 subjects per arm to demonstrate at least a 50% decrease in TT from baseline for "No Go," has been fulfilled as there has been no evidence of TT suppression.

The trial will be run "seamlessly" which means that the transition from Stage 1 to Stage 2 will be conducted without significant interruption and without breaking the study blind. The advantages of the two-stage seamless adaptive design are the efficient use of subjects, increased statistical power for final analysis and more rapid completion of the trial by minimizing the time between the end of Stage 1 and commencement of Stage 2. All data from the Stage 1 will be combined with Stage 2 data for the final analyses after the completion of Stage 2. In Stage 1, there are 10 subjects per arm (a total of 30 subjects).

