# 15. Steering Committee and Data Safety Monitoring Board

The **Steering Committee** will serve as the operational governing board for the project. The Steering Committee will monitor and review reports from the Data Safety Monitoring Board (described below) and any serious AEs. It will oversee the conduct of the trial and progress towards meeting study milestones. It will meet following an award notice and quarterly during the conduct of the trial. The Steering Committee will be chaired by the study PI and will include the CTSI Director, senior statistician, senior pharmacologist, Lilly representative *ex officio*, NIH Project Scientist, NIH Program Officer, and two external scientists with expertise in early stage clinical trials and statistics. The **Steering Committee** will be charged with the review of all relevant data at the end of Stage 1 with the purpose of determining if Go/No go criteria has been met. The relevant data include adverse events considered "probably" and "possibly" related to study drug or study procedure, QTcB values, and TT levels.

Steering Committee, Eli Lilly scientists and NIH scientists and program officers determined that the Stage 1 sample size (10 subjects per arm) was too small to draw conclusions about cortical target engagement and efficacy and therefore these related endpoints will not be considered in the Go/No Go decision. The IU Adult Psychiatry **Data Safety Monitoring Board** (DSMB) will be responsible for data and safety monitoring. DSMB is responsible for reviewing study procedures, AEs, safety mailings (if applicable), enrollment, active subject progress, drop-out rates, and ongoing conduct of the research. The DSMB members can ask questions and make comments and/or recommendations to the investigators. The IRB is notified of significant findings by way of the DSMB meeting minutes at the time of continuing review. DSMB members consist of Department of Psychiatry faculty members who are not investigators on this trial. Data on the number of subjects enrolled and the number of AEs will be reviewed by the Board at least quarterly and more frequently if needed. The resulting report will be issued to the IU IRB at least at the time of continuing review or more frequently by request. Any unanticipated events will be immediately directed to the PI who will follow the IRB reporting procedures.

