The DSMB will be responsible for reviewing all safety and testosterone data for the first 10 subjects treated with 150 mg/day in Stage 2 to determine if it is safe to further randomize subjects to this dose (as described in Section 12 above).

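### Nothing requires allocation to 150 mg/day to close when the fifth confirmed testosterone suppression has already settled the five-of-10 rule

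*Combined protocol and SAP*

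**What the plan says.** Section 12 (Stage 2 Continued Dose Assessment) sets the review: "The first 10 subjects randomized to 150 mg/day will be reviewed by the Data Safety Monitoring Board", to decide whether further randomization to the dose is safe. The drop rule follows: "If five or more of 10 subjects randomized to 150 mg/day meet the TT suppression criteria", the dose leaves Stage 2 and later men are randomized 1:1 to placebo or 75 mg/day. Section 15 restates the Board's duty as "reviewing all safety and testosterone data for the first 10 subjects treated with 150 mg/day in Stage 2".

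On routine monitoring, Section 15 says: "Data on the number of subjects enrolled and the number of AEs will be reviewed by the Board at least quarterly", or more often if needed. Testosterone is not named in that sentence.

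For the individual man, Section 12 (Stage 2 Dosing Downward Titration) says that after a confirmed 50% fall from baseline, "subjects will be blindly switched to the next lowest dosing arm for the remainder of the trial". Section 10 discontinues a man whose suppression persists after the step-down. Section 4 (Addressing Safety in Stage 2) schedules post-randomization testosterone at weeks 1, 2, 4 and 8, and expects suppression to show by week 1.

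**The concern.** A threshold of five among 10 is settled by the fifth case. If that case is confirmed when, say, seven men have started, the results of men eight to 10 cannot reverse the decision. The plan expects suppression to appear early, so the information will often be available in time to use. But no one is told to keep a count, to alert the DSMB at the fifth case, or to hold allocation. If the rule is read as a look at a completed cohort of 10, allocation to 150 mg/day continues until that look.

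At stake is exposure of a few men. The dose exceeds the highest multiple dose previously given, 100 mg/day for 14 days. In the single-dose study, "plasma total testosterone levels demonstrated significant dose-dependent decreases at doses at 25 mg and above". Section 4 names thromboembolic events as a possible consequence of engaging the alpha receptor. A man who starts after the fifth case receives a dose that the plan's own rule has already rejected.

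**Working it through.** **Inputs from the documents.** The threshold is 5 of 10, which matches the 50%-of-arm criterion in Primary Aim 3 (0.50 × 10 = 5). Stage 2 allocation is 70 × (1, 1, 1.5)/3.5 = 20, 20 and 30, as stated. On timing, "Stage 2 will be conducted in years 2 and 3", taken as 24 months, so planned accrual to 150 mg/day is 30/24 = 1.25 men per month.

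**Assumptions.** The documents give no true suppression rate p at 150 mg/day, so a range is shown. They also give no time from a man's start to his confirmation. Two weeks corresponds to the week 1 and week 2 samples, four weeks to the week 2 and week 4 samples, and about nine weeks to a first fall at week 8 plus a one-week retest.

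**Step 1: does closing at the fifth case change the decision?** Under the review at 10, the drop probability is P(X ≥ 5) with X ~ Bin(10, p). Under closure at the fifth case, let K be the position of the man who supplies that case. Then P(K = k) = C(k−1, 4) p^5 (1−p)^(k−5), summed over k = 5 to 10. At p = 0.5 the terms are 0.031 + 0.078 + 0.117 + 0.137 + 0.137 + 0.123 = 0.623, which equals P(X ≥ 5). The two rules agree in every sequence, so the drop probability is the same.

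**Step 2: upper bound with no lag.** If each result were known before the next man started, the mean number spared would be Σ (10−k) P(K = k). At p = 0.5 this is 5(0.031) + 4(0.078) + 3(0.117) + 2(0.137) + 1(0.137) = 1.23.

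**Step 3: with a lag.** Entry gaps are simulated as exponential at 1.25 per month (400,000 sequences). The count is of men among the first 10 who start after the fifth case's start plus the lag, and is zero if five is never reached. Allocation is taken to pause after the tenth man.

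| True rate p | P(dropped) | Mean spared, no lag | 2-week lag | 4-week lag |
|---|---|---|---|---|
| 20% | 0.033 | 0.04 | 0.03 | 0.02 |
| 30% | 0.150 | 0.20 | 0.15 | 0.11 |
| 40% | 0.367 | 0.59 | 0.45 | 0.34 |
| 50% | 0.623 | 1.23 | 0.97 | 0.75 |
| 60% | 0.834 | 2.06 | 1.66 | 1.31 |

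These means average over all trials, including those in which the rule is never met. The chance that at least one man is spared is 42% (2 weeks) or 35% (4 weeks) at p = 0.5, and 65% or 56% at p = 0.6.

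**Step 4: sensitivity.** With a 9-week lag, the mean at 50% falls to 0.36. Over 0.8 to 2.0 men per month and lags of 2 and 4 weeks, it runs from 0.5 to 1.1 at 50% and from 1.0 to 1.8 at 60%. The pause after the tenth man is an assumption that Section 12 does not state. Without it, and with the review waiting the same lag for the tenth man, the lag cancels in expectation and the mean saving returns to the no-lag column.

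**The case against.** The strongest reply is that the drop sentence stands on its own and a fifth confirmed case satisfies it as written. A reader might infer from the review of the first 10 that the plan allows a single look and bars closing the arm before it. The documents do not support that. Neither section says there is only one review or that it must wait for the tenth man, and the Board may meet more often than quarterly. Section 15 also makes the Board responsible for safety monitoring and the ongoing conduct of the research, and gives it the testosterone data for these men. A Board that saw five suppressors would probably act. This part stands, and it reduces the point from a defect to an unassigned step: the Board can act, but nothing ensures that it learns of the fifth case when it happens.

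The evidence on testosterone is also more reassuring than the single-dose result alone suggests. The fall at 25 mg was small (12%), and suppression was reversible in all cases. Multiple doses up to 100 mg/day for 14 days did not suppress testosterone, and Section 4 reports no suppression in blinded Stage 1 data at doses up to 75 mg/day. None of this fixes the rate at 150 mg/day, but it gives no reason to expect 50% or 60%.

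Finally, harm to each extra man is limited. He is sampled at weeks 1 and 2, stepped down once suppression is confirmed and discontinued if it persists. A man who does not suppress shows no alpha engagement on the plan's own marker. A fixed cohort of 10 is a legitimate design. All of this bears on the size of the point. It does not supply the missing trigger.

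**Conclusion.** The point holds as a cheap safety improvement. The five-of-10 rule can be settled before the tenth man starts, and nothing requires a running count or closure of the arm when that happens. On the fixed-cohort reading, men may start a dose that the rule already rejects.

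The size depends on a suppression rate that the documents do not give. With planned accrual and confirmation in 2 to 4 weeks, fewer than 0.2 men are spared on average at rates of 30% or below, and about one to one and a half at 50% to 60%; later confirmation lowers this. The rule exists for the case in which suppression is common, and that is where closure at the fifth case helps. No error rate changes. The finding does not show that the Board would ignore five cases or that the men concerned lack individual protection.

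**What to change.** State in Sections 12 and 15 that allocation to 150 mg/day closes as soon as the fifth confirmed testosterone suppression occurs among the first 10 men randomized to that dose. Whoever carries out the blinded downward switch keeps the count and reports it to the DSMB. The review at 10 stays for the case where five is not reached.

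The cost is a sentence or two of text and a running unblinded count. The documents name no such role, but the blinded switch already needs someone who knows the man's arm at each confirmed case. If the arm closes early, slightly fewer men contribute at 150 mg/day. Given that the rule is met at a 50% rate, this is about 0.75/0.623 = 1.2 to 0.97/0.623 = 1.6 men. The analysis affected is the dose-concentration-response analysis, which Section 16 makes secondary once the dose is dropped. Those men go to placebo or 75 mg/day, so the Stage 2 total of 70 can stand.
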